7. SAFETY ASSESSMENTS

7.1: Specification of Safety Parameters

Low level laser devices used for the purposes of photobiomodulation or acupuncture are designated by the FDA as “non-significant risk” devices (37). After four decades of research, over 4000 peer-reviewed papers and over 150 Phase III clinical trials, there are no known side effects attached to low level laser therapy (LLLT). Animal studies have shown that lasering the head, or transcranial photobiomodulation (tcPBM), is very safe and causes no thermal or neoplastic changes in the cortex(38). The use of tcPBM has been shown to have promise for treating traumatic brain injury(39-41) and stroke(42-44), as well as enhancing mood(45-47) and cognition(48-52) in humans.

CLRT involves principles and laser dosages very similar to laser acupuncture. Laser acupuncture has been extensively studied and deemed to be safe and effective for certain musculoskeletal conditions(21), especially in long-term follow up (29). No known or anticipated serious side effects from CLRT have yet occurred but minor reactions may include mild delayed onset muscle soreness or headache. Due to the intensity of the laser light, subjects will wear proper eye protection that blocks the specific wavelength of light while lasers are in use.

Based on previous research, no serious side effects are anticipated. The PI will closely monitor all subjects for any adverse events and will report them to the IRB if any arise.

Examples of safety measures include: monitoring subjects for any discomfort related to intervention; reports of cramps, spasms, headache or delayed onset muscle soreness.

7.2: Methods and Timing for Assessing, Recording, and Analyzing Safety Parameters

- 1) Timing: each contact with the subject will be an opportunity to inquire about adverse events.
- 2) Recording: each incidence of an adverse event will be recorded in the case report form in a designated location for this information.
- 3) Analyzing: the PI will be informed of all adverse events and will forward the information to the IRB.

7.3: Adverse Events (AEs) and Serious Adverse Events (SAEs)

Definitions

An adverse event (AE) is any untoward medical occurrence in a subject during participation in the clinical study. An adverse event can include a sign, symptom, abnormal assessment (laboratory test value, vital signs, electrocardiogram finding, etc.), or any combination of these.

A serious adverse event (SAE) is any AE that results in one or more of the following outcomes:

- Death
- A life-threatening event
- Inpatient hospitalization or prolongation of existing hospitalization
- A persistent or significant disability/incapacity
- A congenital anomaly or birth defect
- An important medical event based upon appropriate medical judgment

Classification of AE Severity

Classification of AEs will be based on the Common Terminology Criteria for Adverse Events (CTCAE) Version 4, 2009. AEs will be described by symptom or condition/diagnosis, and graded for severity (mild, moderate, or severe), depending on the intensity of the event. Two additional categories will be used based on the CTCAE system, “life threatening” and “death”.

Grade 1. Mild: asymptomatic or mild symptoms; clinical or diagnostic observations only; minimal impact on subject’s life; intervention not indicated.

Grade 2. Moderate: medical care sought; significant but limited inconvenience on Activities of Daily Living (ADL) or lifestyle; local or noninvasive intervention indicated.

Grade 3. Severe: medically significant but not immediately life-threatening; disabling; limiting self-care; substantial disruption to the subject’s well-being; hospitalization or prolongation of hospitalization indicated.

Grade 4. SAE. Life-threatening consequences; urgent medical intervention indicated.

Grade 5. SAE. Death: related to AE.

An AE that is graded as severe (Grade 3) can be distinct from an SAE (Grades 4 and 5). A subject could experience a severe AE (Grade 3) that does not meet the definition of an SAE (see above). Alternatively, a subject could experience a moderate AE (fever, mild confusion) that meets the SAE definition (example - need for antibiotics to combat a life threatening infection).

AE Attribution Scale

AEs will also be classified on an assessment of relatedness to the study intervention. AEs will be categorized according to the likelihood that they are related to the study intervention. They will be labeled as: 1) definitely related, 2) definitely unrelated, 3) probably related, or 4) possibly related to the study intervention in the opinion of the PI after review of the circumstances and relevant records. Attributions will be made by the PI.

7.4: Reporting Procedures

Those events that will be asked about (solicited) include: delayed onset muscle soreness and pain in the hamstring. Other events that could occur with maximal contraction of the hamstring strength test include fatigue, cramps, spasms, muscle strain, or muscle pain.

Unsolicited events will be captured by query at each visit after enrollment.

Time frames for reporting and collecting AEs are weekly. Reporting of AEs must be to the IRB and OHRE. For SAEs the time frame is daily reporting and capture as soon as possible.

Detection of AEs and SAEs will be the responsibility of each member of the research team at every subject contact. Reporting procedures for unexpected events related to the study intervention will include written documentation of the finding or complaint, which will occur within 5 days for AEs and immediately or as soon as possible for SAEs. The goal of reporting is to inform the PI for a determination of severity, relatedness to the research, and next level of reporting, i.e. IRB, TraCS Institute.

Decisions regarding relatedness and severity will be made by the PI once all available information has been reviewed.

Safety Monitor members will be informed of AEs and SAEs as part of their routine reviews.

Case Report Forms will be used to collect AE and SAE data entered into a secure database.

Reports will be distributed to the PI and Co-I's and Project Manager. These reports will be coded and without identifiers.

7.5: Follow up for Adverse Events

Subjects who have experienced AEs will be followed until resolved or considered stable by the PI. For issues not resolved, a minimum period of follow up is 1 month with contact on a weekly basis by telephone or in person.

7.6: Safety Monitoring

The senior advisors on this study will serve as data and safety monitors and make up the Data and Safety Committee: [name], [name], and [name]. We will record all adverse events and unexpected health problems and review weekly with the study team. Safety monitors will review the adverse events and unexpected health problems after the tenth subject reaches visit 2 in the intervention and every 3 months thereafter.

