9.4: Interim Analyses and Stopping Rules

We are not planning any pre-specified interim analyses for any reason. The study may be suspended by our PI or the Data and Safety Monitoring Committee (DSMC) if a severe adverse event occurs that is deemed to be secondary to the intervention. The DSMC may also suspend or stop the study or a study arm if reported adverse events are increasing, either across intervention arms or in a particular study arm.

9.5: Outcomes

Outcomes include two functional measures that will be logged into REDCap at the time of the evaluation. The study coordinator will verify complete data entry after each study visit.

9.5.1: Primary Outcome

We define the primary outcome as the change in angle of the KEA test from the time before to the intervention to afterwards.

9.5.2: Secondary Outcomes

We define the secondary outcome as the difference in peak hamstring strength on HHD, and difference in PPT scores between pre and post-intervention time periods.

Subgroup analyses: conduct analyses on the primary outcome stratifying on gender and baseline hamstring subjective tightness, flexibility and strength, number of prior hamstring injuries.

9.6: Data Analyses

To compare mean KEA response between treatment conditions, we will use a linear mixed effect model. The model will include fixed effects for treatment, period, and baseline pre-intervention KEA within each period. The model will include random subject effects to account for correlation between repeated measurements. Given the length of the washout period relative to the treatment period, the primary analysis will assume no carry-over effects and will estimate effect size along with a 95% confidence interval. As a secondary analysis to explore the potential for carry-over, we will include and test a fixed effect for treatment-by-period interaction. If significant carry-over is identified, we will also report comparisons using only the period 1 data. We will use a similar approach to explore intervention effects on HHD and PPT.

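### No summary of adverse events by treatment received is planned, so soreness from CLRT could not be told apart from muscle symptoms caused by the strength test

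*Combined protocol and SAP*

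**What the plan says.** Section 7.1 says of CLRT that "minor reactions may include mild delayed onset muscle soreness or headache". Section 7.4 sets what participants are asked about: "Those events that will be asked about (solicited) include: delayed onset muscle soreness and pain in the hamstring". The next sentence turns to the strength test: "Other events that could occur with maximal contraction of the hamstring strength test include fatigue, cramps, spasms, muscle strain, or muscle pain".

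Section 7.2 has three items: timing, recording and analysis. The third reads, in full, "Analyzing: the PI will be informed of all adverse events and will forward the information to the IRB". On relatedness, Section 7.3 says "Attributions will be made by the PI", and Section 7.4 repeats that the PI decides relatedness and severity. Section 9.6 specifies a mixed model for KEA and closes with "We will use a similar approach to explore intervention effects on HHD and PPT". It does not mention adverse events.

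There is further oversight. Section 7.6 says "We will record all adverse events and unexpected health problems and review weekly with the study team", and "Safety monitors will review the adverse events and unexpected health problems after the tenth subject reaches visit 2", with further monitor reviews every three months. Section 9.4 lets the DSMC suspend or stop the study or an arm if adverse events are rising overall or in one arm.

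**The concern.** The item that should describe an analysis describes a reporting route. A participant with a sore hamstring after a visit has had both a laser session (active or sham) and repeated maximal contractions, and the protocol itself expects overlapping muscle symptoms from both. Nothing about the single case identifies the cause. What can identify it is how often the same complaint follows the sham session, where the testing is the same. The crossover collects that information in each completer, but no section uses it for safety.

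At stake is the tolerability statement from what Section 2.2 calls the first clinical trial to examine these effects of CLRT directly in people. Judged case by case, test soreness could be counted as a CLRT reaction, or a CLRT reaction dismissed as test soreness. The study-wide stopping provision in Section 8 also counts events judged to be due to the intervention, so it relies on the same judgement.

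**Working it through.** **1. The plan's own numbers.** The documents give no adverse-event rate. The only figures to reproduce are those that fix the number of participants (Section 9.2): difference 5°, SD 15°, correlation 0.75, two-sided 0.05.
- SD of the within-person difference = 15 × √(2 × (1 − 0.75)) = 10.61.
- Paired t power is 79.7% with 37 and 80.8% with 38, so the stated 38 reproduces.
- 38 / 0.9 = 42.2, rounded up to 43, against 44 stated.

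These figures are not in dispute. They give n = 38 completers and 44 enrolled for what follows.

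**2. Test load under each treatment.** HHD is the mean of three attempts (Section 3), done before and after the intervention at each visit (Section 6.2.4). That is 3 × 2 = 6 maximal efforts per visit, the same under CLRT and sham. Symptoms caused by the test should therefore occur equally often under both.

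**3. Does any provision compare treatments?**
- Section 7.2: informs and forwards; no summary.
- Section 7.3: a relatedness category for each event; no denominator and no comparator.
- Section 7.6: weekly and periodic review; content not specified by treatment.
- Section 9.4: implies a look by arm, but gives no rate, method, table or rule for assigning an event to a treatment. Every completer receives both treatments, so such a rule is needed.
- Appendix C.a: one cumulative form per participant, with start and stop dates but no period or treatment field.
- Section 9.6: efficacy outcomes only.

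**4. What case-by-case judgement could do (assumed rates).**
- No CLRT effect, test soreness in 10% to 30% of participants per visit: 38 × 0.10 = 3.8 to 38 × 0.30 = 11.4 participants sore after CLRT (4.4 to 13.2 of 44). Any of these attributed to CLRT is an error.
- Test soreness 20%, true CLRT excess 20 points: 38 × 0.40 = 15.2 sore after CLRT and 38 × 0.20 = 7.6 after sham, a true excess of 7.6. Attribution of the CLRT-period cases could return anything from 0 to 15.2. The difference between periods has expectation 7.6.

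**5. Precision of the paired comparison.** With sham rate p0, CLRT rate p1 and within-person correlation ρ:
- p11 = p0·p1 + ρ·√(p0(1−p0)p1(1−p1)); b = p1 − p11; c = p0 − p11.
- 95% half-width = 1.96 × √((b + c − (p1 − p0)²)/n).
- Example: p0 = 0.20, p1 = 0.40, ρ = 0, n = 38. Then p11 = 0.08, b = 0.32, c = 0.12, and the half-width is 1.96 × √((0.44 − 0.04)/38) = 0.201, about 20 points.
- Range for p0 of 10% to 30%, excess of 10 to 30 points, ρ of 0 to 0.3, and n of 38 or 44: 12.5 points (p0 = 0.10, p1 = 0.20, ρ = 0.3, n = 44) to 21.6 points (p0 = 0.30, p1 = 0.50, ρ = 0, n = 38).
- Exact McNemar power over the same grid: 10% to 21% for a 10-point excess, 34% to 72% for 20 points, 67% to 97% for 30 points.

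**The case against.** The case on the other side is substantial, and much of it stands as a limit on the point.

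- A reader might infer that adverse events are merely passed on and never looked at by treatment. Sections 7.6 and 9.4 do not support that: there are two layers of review and a power to act on one arm. What is missing is a specified summary.
- A reader might infer that an established harm of CLRT will be misreported. Section 7.1 speaks only of possible minor reactions, and says low-level laser therapy has no known side effects. Relatedness is graded, not yes or no, and nothing says that results will be reported by attribution alone.
- A reader might infer biased attribution, since Section 2.1 says the PI developed CLRT. The treating investigator is unmasked (Section 3), but the documents do not say that this is the PI. Section 6.2.3 has the PI told the allocation when the blind is broken, which suggests the PI may otherwise be masked. Bias is possible but not established.
- Delayed onset soreness is not itself in the strength-test list. The link comes from the words introducing that list and from the overlap with muscle pain.
- The rates above are assumptions, and the start dates and treatment assignments needed for a table will exist anyway, so it could still be made at reporting.

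The last argument shows that the fix is cheap, not that the plan contains it. A comparison chosen after the events are known is weaker than one written down beforehand. None of these objections supplies a by-treatment summary.

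**Conclusion.** The point holds in this form: the plan specifies no summary of adverse events by treatment received, so soreness that may come from CLRT could not be separated from muscle symptoms that come from testing, and error is possible in either direction. This rests on the text of Sections 7.1 to 7.6, 9.4 and 9.6 and on identical testing under both treatments, not on any assumed rate.

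The size cannot be fixed from the documents. Under the assumed 10% to 30% background, about 4 to 11 of 38 participants would be sore after CLRT without any CLRT effect. A paired estimate would carry about 12 to 22 points either side.

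The primary and secondary efficacy conclusions are not affected. The change is worth making because it replaces a stated reporting step with a randomised comparison at almost no cost.

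**What to change.** In Section 7.2 item 3, with a matching paragraph in Section 9.6:

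- Assign each adverse event to the treatment given at the last session before its start date. The form records a date and no time, so for an event dated on a visit day, note whether it began before or after that day's intervention.
- Tabulate the number and percentage of participants with soreness, hamstring pain, headache and any adverse event after CLRT and after sham. Use as denominator all participants who received that treatment, so that those who attend one visit are counted.
- For participants with both periods, give the paired risk difference with a 95% CI, labelled descriptive.
- Show the PI's attribution beside these figures, not in place of them. The relatedness scale has four levels in Section 7.3, five in Appendix C.a and three in Appendix C.b, and these need reconciling before attribution can be tabulated.
- State that headache is named as a possible reaction in Section 7.1 but is not in the solicited list in Section 7.4, so its capture may differ from that of soreness.

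The cost is a few lines of text, one table and the before-or-after note. Start dates and the treatment sequence are already recorded, and no treatment, stopping or clinical provision changes. The downside is wide intervals: a CI that includes zero must not be read as showing that CLRT causes no soreness.

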8. INTERVENTION DISCONTINUATION

Discontinuation of intervention for a participant: Subject may stop their participation for any reason, e.g., the subject is non-compliant with the protocol; subject develops unacceptable side effects; or psychosocial circumstances prevent continuation.

Possible reasons for discontinuation of the whole study: Study closure by NC TraCS; research environment is no longer supportive; multiple Unexpected Problems (UP); insufficient recruitment to answer research hypotheses. If greater than 3 enrolled and randomized subjects develop a grade 3 or greater adverse event due to the intervention, the entire study would be stopped and the safety monitors would reevaluate.

Early discontinuation: Participants will continue to be followed, with their permission, for another 6 weeks if study interventions are discontinued for reasons other than the normal end of the study.

Normal end to the study: Subjects completing the final evaluation will be followed up one week after the final visit by phone call to solicit any possible AEs.

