Appendix C.a: Adverse Event Form (version 1.0)

Adverse Event Form

Cranial Laser Reflex Technique for Hamstring Flexibility, Strength and Pain

Pilot trial supported by NC TrACS and NCCIH

Site Name: University of North Carolina-Chapel Hill, Program on Integrative Medicine, Dept. of Physical Medicine and Rehabilitation

Subject ID: _____

This form is cumulative and captures adverse events of a single participant throughout the study.

Severity	Study Intervention Relationship	Action Taken Regarding Study Intervention	Outcome of AE	Expected	Serious Adverse Event (SAE)
1 = Mild 2 = Moderate 3 = Severe 4 = Life-Threatening	0 = Not related 1 = Unlikely related 2 = Possibly related 3 = Probably related 4 = Definitely related	0 = None 1 = Dose modification 2 = Medical intervention 3 = Hospitalization 4 = Intervention discontinued 5 = Other	1 = Resolved 2 = Recovered with minor sequelae 3 = Recovered with major sequelae 4 = Ongoing/Continuing treatment 5 = Condition worsening 6 = Death 7 = Unknown	1 = Yes 2 = No	1 = Yes 2 = No (If yes, complete SAE form)

Adverse Event	Start Date	Stop Date	Severity	Relationship	Action Taken	Outcome of AE	Expected?	SAE?

At end of study only, check this box if participant had no adverse events: ☐ None

Signature /Print name

Date

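### Section 7.1 names headache as a possible CLRT reaction, but the solicited list in 7.4 omits it, so headache may be under-ascertained

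*Combined protocol and SAP*

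**What the plan says.** Section 7.1 states that "minor reactions may include mild delayed onset muscle soreness or headache". Its examples of safety measures include watching for "reports of cramps, spasms, headache or delayed onset muscle soreness". Headache therefore appears twice in 7.1, once as an anticipated reaction and once as something to monitor.

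Section 7.4 sets out what subjects are asked about by name: "Those events that will be asked about (solicited) include: delayed onset muscle soreness and pain in the hamstring". A second list follows, tied to the strength test: "Other events that could occur with maximal contraction of the hamstring strength test include fatigue, cramps, spasms, muscle strain, or muscle pain". Neither list contains headache.

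For everything else there are general routes:
- Section 7.4: "Unsolicited events will be captured by query at each visit after enrollment".
- Section 7.2: "each contact with the subject will be an opportunity to inquire about adverse events".
- Section 8: subjects who complete the study are "followed up one week after the final visit by phone call to solicit any possible AEs".

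Events go on the form in Appendix C.a, which states: "This form is cumulative and captures adverse events of a single participant throughout the study". As shown, it has free-text rows and no symptom checklist.

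**The concern.** The protocol itself separates solicited from unsolicited events, and headache falls on the unsolicited side. Both named prompts are muscle events, which maximal contraction testing could produce in either condition. Of the two reactions that 7.1 names, headache is the one that matches the site of application, because Section 3 has the probe touching the scalp.

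A symptom asked about by name and one that depends on a general question are not necessarily recorded equally well. If headache is captured less completely, its absolute rate would look lower than it is, and soreness and headache could not be compared on equal terms. A report of few or no headaches would be hard to interpret, since it could reflect either tolerability or the way the question was put.

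**Working it through.** **1. The places that could supply a headache prompt**

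| Place | What it provides | Headache asked by name? |
|---|---|---|
| 7.1 | Possible reactions; examples of monitored reports | Named, but not as a question |
| 7.4, solicited list | Delayed onset soreness, hamstring pain | No |
| 7.4, second list | Strength-test events | No |
| 7.4 and 7.2, general query | Any event, at visits and contacts | Not specified |
| 8, phone call | Any event, one week after the final visit | Not specified |
| 6.1, schedule of evaluations | No adverse-event row; a Week 3 follow-up entry | No |
| 6.2.4, visit lists | No adverse-event question | No |
| 10.3.1, contents listed for the operating manual | Consent forms and functional tests | No |
| Appendix C.a | Free-text rows | No |

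Section 7.4 is thus the only place in these documents that says which symptoms are asked about by name, and headache is not among them.

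**2. Timing**

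Visits are ideally one week apart (6.2.4). A headache that starts after the subject leaves Visit 1 is next asked about at Visit 2. One that starts after Visit 2 waits for the phone call a week later. In both cases capture depends on recall over about a week, in answer to a general question.

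**3. Scale (illustration only)**

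The plan has no figure to reproduce here. Inputs:
- N = 44, the number to be enrolled (9.2), taken as all receiving CLRT.
- p, the true proportion with a headache after CLRT: assumed, 2% to 20%.
- c, the share of those headaches that the general query captures: assumed, 25% to 100%.

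Expected number of subjects recorded with headache = N × p × c. Chance of recording none = (1 − p × c)^N.

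With p = 10% and c = 50%, the expected number is 44 × 0.10 × 0.50 = 2.2, and the chance of none is (1 − 0.05)^44 = 0.105. Each cell below gives the expected number, then the chance of none.

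| p | c = 100% | c = 75% | c = 50% | c = 25% |
|---|---|---|---|---|
| 2% | 0.88; 0.411 | 0.66; 0.514 | 0.44; 0.643 | 0.22; 0.802 |
| 5% | 2.20; 0.105 | 1.65; 0.186 | 1.10; 0.328 | 0.55; 0.575 |
| 10% | 4.40; 0.010 | 3.30; 0.032 | 2.20; 0.105 | 1.10; 0.328 |
| 20% | 8.80; <0.001 | 6.60; 0.001 | 4.40; 0.010 | 2.20; 0.105 |

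The first column is the case where the general query misses nothing, and there the omission costs nothing. At p = 2% the chance of seeing no headache is already 0.411 with full capture, so a prompt cannot make a rare event estimable in a trial of this size.

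**4. Comparison between conditions**

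Let the true rates be p₁ under CLRT and p₀ under sham, with the same capture share c in both. The recorded difference is c × (p₁ − p₀) and the recorded ratio is p₁ / p₀. With assumed rates of 10% and 5% and c = 50%, the recorded rates are 5% and 2.5%. The difference shrinks from 5 to 2.5 percentage points, the ratio stays at 2, and the direction is unchanged.

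**The case against.** The strongest reply is that headache is actively sought. There is a query at each visit, every contact is an occasion to ask, 7.4 makes detection the duty of each team member, and Section 8 adds a call for any event. Section 3 also plans direct contact at each visit to ease adverse-event reporting. Section 7.1 lists headache for monitoring, and the solicited list is introduced with a word that leaves it open. Subjects and assessors are blinded, and the same query follows both conditions.

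Most of this stands, and it limits the point. What it does not do is tell staff to ask about headache by name, or reconcile the two sections.

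A reader might go further in three ways that the documents do not support:
- **That headache will be under-counted because it rests on volunteered reports.** A planned open query is weaker than a named prompt, but it is not reliance on volunteering. Under-counting is a risk and has not been shown.
- **That this is the first trial of laser on the head, which makes headache its main tolerability result.** Section 2.2 claims only the first trial to examine directly these particular effects of CLRT. Section 7.1 cites human transcranial work, and the reference list includes an earlier randomized CLRT trial and a phase III transcranial laser trial in stroke. Sections 9.5 and 9.6 define no safety outcome and no headache comparison.
- **That the CLRT-sham comparison is biased.** The omission applies equally to both conditions and does not by itself produce bias in either direction.

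**Conclusion.** The point holds as a minor inconsistency in safety data collection. Section 7.1 anticipates and monitors headache, 7.4 does not solicit it, and no schedule, visit list or form in the documents fills the gap. Headache may therefore be under-ascertained relative to soreness and hamstring pain. What is mainly at risk is the absolute headache count. If capture is equal in the two conditions, the absolute difference would shrink in proportion while its direction is kept.

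The size is unknown. The table above rests wholly on assumed headache rates and capture shares, and it includes the case of no loss. The primary outcome, its analysis and the sample size do not depend on this point.

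**What to change.** Reconcile 7.4 with 7.1 by adding headache to the solicited list, and carry the question into the schedule in 6.1 and the visit lists in 6.2.4.

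- Ask in identical words after both conditions, at contacts already planned: the same day after treatment at each visit, the start of Visit 2, and the Week 3 call.
- Put the same-day question after the post-treatment tests and the de-blinding questionnaire, so that it does not cue either.
- Tabulate headache by the treatment received in that period. Events reported at the start of Visit 2 belong to the first period. The start date on the adverse-event form allows the allocation.

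The cost is one extra question per contact and a somewhat higher count of background headaches in both conditions. The sham period gives the reference against which to read that background.
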